2.3. Benefit: Risk Assessment

Tofacitinib, as noted above and in the tofacitinib IB, has a number of important and potentially important safety risks that include serious and other infections, malignancies (excluding NMSC), a potential for GI perforations, blood and lymphatic system disorders, drug hypersensitivity, and MACE (including VTE). Tofacitinib also has a number of monitorable effects on laboratory values, including both hematology and clinical chemistry parameters. Given the totality of efficacy and safety data, the overall benefit: risk relationship for approved doses of tofacitinib (including, 5 mg IR BID and 11 mg MR QD) continues to remain favorable.

PF-06651600 is a selective inhibitor of a member of the JAK family and, therefore, may (or may not) have a safety profile distinct from other, less selective JAK inhibitors. However, until more clinical trial data are available for it and other selective JAK inhibitors, a risk profile similar to other JAK inhibitors for which more data are available cannot formally be excluded. Therefore, as noted above and in the PF-06651600 IB, based on the current clinical and nonclinical experience with PF-06651600 and other JAK inhibitors, the potential risks for PF-06651600 include: viral reactivation; serious infections and opportunistic infections; malignancy and lymphoproliferative disorders; decreased lymphocyte counts; change in neutrophil counts; decreased platelet count; alterations in the lipid profile; and dermatologic effects (rash/acne); and thromboembolism. Given the efficacy seen in the Phase 2 RA study and in Phase 2/3 studies in alopecia areata and vitiligo, the potential benefit: risk of PF-06651600 in RA at proposed doses appears favorable.

To date, no safety risks or potentially important safety risks have been identified for PF-06650833. However, based on nonclinical and clinical data, and theoretical considerations derived from its mechanism of action as a modulator of innate immune signaling, effects of PF-06650833 on rates of infection, including serious and other infections, renal function, and liver transaminases are possible. The accumulated safety data and the efficacy demonstrated in the Phase 2 study in RA are consistent with a potentially favorable benefit: risk relationship for PF-06650833 in RA.

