7.2. Participant Discontinuation/Withdrawal From the Study

A participant may withdraw from the study at any time at his/her own request or may be withdrawn at any time at the discretion of the investigator for safety, behavioral, compliance, or administrative reasons.

At the time of discontinuing from the study, if possible, an early withdrawal (EW) visit should be conducted. See the [SoA](#) for assessments to be collected at the time of study discontinuation and follow-up and for any further evaluations that need to be completed.

The early discontinuation visit applies only to participants who are randomized and then are prematurely withdrawn from the study. Participants should be questioned regarding their reason for withdrawal. The participant will be permanently discontinued both from the study intervention and from the study at that time.

If a participant withdraws from the study, he/she may request destruction of any remaining samples, but data already generated from the samples will continue to be available, and may be used to protect the integrity of existing analyses. The investigator must document any such requests in the site study records.

If the participant withdraws from the study and also withdraws consent (see below) for disclosure of future information, no further evaluations should be performed, and no additional data should be collected. The sponsor may retain and continue to use any data collected before such withdrawal of consent.

When a participant withdraws from the study because of an SAE, the SAE must be recorded on the CRF and reported on the Clinical Trial (CT) SAE Report.

Lack of completion of all or any of the withdrawal/early termination procedures will not be viewed as protocol deviations so long as the participant's safety was preserved.

The Sponsor's clinical team should be consulted as soon as possible if a participant is being considered for or has been discontinued from study treatment for an adverse event or other safety issue.

Participants interrupting study medication for more than 7 consecutive days (either due to lack of compliance or in response to an AE), or patients who are less than 80% compliant with the dosage regimen for any 2 consecutive visit periods should be withdrawn from the study. Upon discontinuation of the study treatment, participants will enter a FU period of 4 weeks, after which they will complete the FU/EOS visit and will be withdrawn from the study.

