Any participant who meets discontinuation criteria as specified in [Section 8.10](#) should be discontinued from the study.

ECG Changes

A participant who meets either of the bulleted criteria based on the average of triplicate ECG readings will be withdrawn from the study.

- QTcF >500 msec.

- Change from baseline: QTc >60 msec.

If a clinically significant finding is identified (including, but not limited to, changes from baseline/randomization in QTcF after enrollment), the investigator or qualified designee will determine if the participant can continue in the study and if any change in participant management is needed. This review of the ECG printed at the time of collection must be documented. Any new clinically relevant finding should be reported as an AE.

See the [SoA](#) for data to be collected at the time of intervention discontinuation and follow-up and for any further evaluations that need to be completed.

Withdrawal of Consent:

Participants who request to discontinue receipt of study treatment will remain in the study and must continue to be followed for protocol-specified follow-up procedures. The only exception to this is when a participant specifically withdraws consent for any further contact with him or her or persons previously authorized by the participant to provide this information. Participants should notify the investigator in writing of the decision to withdraw consent from future follow-up, whenever possible. The withdrawal of consent should be explained in detail in the medical records by the investigator, as to whether the withdrawal is only from further receipt of investigational product or also from study procedures and/or posttreatment study follow-up, and entered on the appropriate CRF page. In the event that vital status (whether the participant is alive or dead) is being measured, publicly available information should be used to determine vital status only as appropriately directed in accordance with local law.

Participants who discontinue receipt of treatment due to lack of response will be discontinued from this study and will be treated for their RA according to local standard of care (SoC) practice. Upon discontinuation of the study treatment, participants will enter a FU period of 4 weeks, after which they will complete the FU/EOS visit and will be withdrawn from the study.

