8. STUDY ASSESSMENTS AND PROCEDURES

The investigator (or an appropriate delegate at the investigator site) must obtain a signed and dated ICD before performing any study-specific procedures.

Study procedures and their timing are summarized in the [SoA](#). Protocol waivers or exemptions are not allowed.

Immediate safety concerns should be discussed with the sponsor immediately upon occurrence or awareness to determine if the participant should continue or discontinue study intervention.

Adherence to the study design requirements, including those specified in the [SoA](#), is essential and required for study conduct.

All screening evaluations must be completed and reviewed to confirm that potential participants meet all eligibility criteria. The investigator will maintain a screening log to record details of all participants screened and to confirm eligibility or record reasons for screening failure, as applicable.

Every effort should be made to ensure that protocol-required tests and procedures are completed as described. However, it is anticipated that from time to time there may be circumstances outside the control of the investigator that may make it unfeasible to perform the test. In these cases, the investigator must take all steps necessary to ensure the safety and well-being of the participant. When a protocol-required test cannot be performed, the investigator will document the reason for the missed test and any corrective and preventive actions that he or she has taken to ensure that required processes are adhered to as soon as possible. The study team must be informed of these incidents in a timely manner.

For samples being collected and shipped, detailed collection, processing, storage, and shipment instructions and contact information will be provided to the investigator site prior to initiation of the study.

Blood samples may be taken for safety assessments at times specified by Pfizer, provided the total volume taken during the study does not exceed 550 mL during any period of 60 consecutive days.

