8.10. Triggered Requirements

Triggered requirements are specified in the Table in [Section 8.11](#).

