8.11. Guidelines for Monitoring and Discontinuations

Condition	Action
Renal function	
Any serum creatinine increase >50% over the average of screening (most recent value prior to baseline) and baseline values OR an absolute increase in serum creatinine >0.3 mg/dL (>26.5 µmol/L) over the average of screening (most recent value prior to baseline) and baseline values.	The participant should return to the study site for prompt retesting, ideally within 3-5 days . If the second assessment (after the 1 st observations of ≥0.3 mg/dL (or ≥26.5 µmol/L) in serum creatinine relative to study participants' own baseline measurement) is ≥0.4 mg/dL (or ≥35.4 µmol/L), the subject should be discontinued from the study and adequate, immediate, supportive measures taken to correct apparent acute kidney injury. Participant followed until resolution or deemed medically stable by PI.
Liver Function	
2 sequential AST or ALT elevations ≥3 x ULN with a total bilirubin value ≥2 x ULN.	Treatment with all study drugs will be discontinued and the participant withdrawn from this study. Participant followed until resolution or deemed medically stable by PI.
2 sequential AST or ALT elevations ≥3 x ULN with an elevated INR.	Treatment with all study drugs will be discontinued and the participant withdrawn from this study. Participant followed until resolution or deemed medically stable by PI.
2 sequential AST or ALT elevations ≥3 x ULN accompanied by symptoms consistent with hepatic injury.	Treatment with all study drugs will be discontinued and the participant withdrawn from this study. Participant followed until resolution or deemed medically stable by PI.
2 sequential AST or ALT elevations ≥5 x ULN, regardless of Total Bilirubin or accompanying symptoms.	Treatment with all study drugs will be discontinued and the participant withdrawn from this study. Participant followed until resolution or deemed medically stable by PI.
Any single AST and/or ALT elevation >3 times the upper limit of normal (ULN).*	The participant should return to the study site for prompt retesting, ideally within 3-5 days.*

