6.3.2. Laboratory Data

To determine if there are any clinically significant laboratory abnormalities, the safety laboratory tests will be assessed against the criteria specified in the protocol. The assessment will consider whether each participant's baseline test result is within or outside the laboratory reference range for the laboratory parameter. Absolute value, changes from baseline and percent changes from baseline in laboratory data will be summarized. The number (%) of subjects with abnormal AST, ALT, and alkaline phosphatase ($>2 \times$ ULN), and bilirubin ($>1.5 \times$ ULN) and the number (%) of subjects with abnormal AST, ALT, and alkaline phosphatase ($>2 \times$ baseline) will also be presented. Baseline of safety laboratory tests will be the last pre-dose measurement.

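### The renal row of Protocol Section 8.11 triggers a retest against one creatinine reference but conditions the stop on another; read literally, this can delay a stop by about one retest cycle

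*Protocol*

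**What the plan says.** The renal row of the table in Protocol Section 8.11 has two cells.

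- **Condition cell.** A retest is called for when serum creatinine rises by more than 50%, or by more than 0.3 mg/dL, in each case "over the average of screening (most recent value prior to baseline) and baseline values". The retest should ideally take place within 3-5 days.
- **Action cell.** The participant is to be discontinued, with supportive measures for apparent acute kidney injury, if the second assessment shows a rise of at least 0.4 mg/dL. A parenthesis says that this assessment follows first observations of at least 0.3 mg/dL. The end of the parenthesis and the stop level read "relative to study participants' own baseline measurement) is ≥0.4 mg/dL".

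The row is operative. Section 7.2 ("Any participant who meets discontinuation criteria as specified in") points to Section 8.10 and says such participants should be discontinued; Section 8.10 ("Triggered requirements are specified in the Table in") passes the reader on to Section 8.11.

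No section says that own baseline means the screening/baseline average. SAP Section 6.3.2 states: "Baseline of safety laboratory tests will be the last pre-dose measurement".

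**The concern.** The two cells differ in three ways. The trigger uses an average of two values, while the stop's precondition uses own baseline. The trigger has a 50% route and the precondition has none. The trigger needs a rise above 0.3 mg/dL, while the precondition needs at least 0.3. The reference for the 0.4 mg/dL retest level is also not stated cleanly, because own baseline appears only inside the parenthesis.

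A participant may therefore enter the retest pathway by a route that the stop does not recognise. Two sites with identical creatinine values could act differently on a level that the row itself treats as apparent acute kidney injury. Renal safety is a named interest: for PF-06650833, Section 2.3 says effects on "renal function, and liver transaminases are possible", and the drug is given in three of the five arms, including both combinations.

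**Working it through.** **Inputs.** The thresholds (50%, 0.3, 0.4 mg/dL) and the 3-5 day retest come from Section 8.11. The row's paired units agree: 26.5/0.3 = 88.3 and 35.4/0.4 = 88.5 µmol/L per mg/dL. The documents give no within-person creatinine variability, so the creatinine values below are assumptions in mg/dL, taken as reported to 0.01. Screening can last up to 28 days (Section 4.1), so the two pre-dose values can differ.

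**Notation.** S = screening, B = baseline, A = (S + B)/2.
- Trigger: first value > 1.5 × A, or first value > A + 0.3.
- Literal stop: first value ≥ B + 0.3, and then retest ≥ B + 0.4.

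**Case (a): baseline above screening.** First values above A + 0.3 but below B + 0.3 trigger a retest and miss the precondition. The band has width B − A = (B − S)/2, which is 0.025, 0.05 and 0.10 for differences of 0.05, 0.10 and 0.20.
- S = 0.70, B = 0.80, A = 0.75.
- First value 1.08: 1.08 − 0.75 = 0.33, so a retest is triggered; 1.08 − 0.80 = 0.28, so the precondition is missed.
- Retest 1.22: 1.22 − 0.75 = 0.47 and 1.22 − 0.80 = 0.42. The rise is at least 0.4 on either reference, but there is no literal stop.

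**Case (b): the 50% trigger at low creatinine.** With S = B = A, a rise above 50% that is also below 0.3 needs 0.5 × A < 0.3, so A < 0.6.
- S = B = 0.50. First value 0.76: 0.76/0.50 = 1.52 (+52%) and 0.76 − 0.50 = 0.26. A retest is triggered and the precondition is missed.
- Retest 0.92: 0.92 − 0.50 = 0.42, with no literal stop.
- S = B = 0.55 behaves the same way: first 0.84 (+52.7%, +0.29), retest 0.96 (+0.41).

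Because S = B here, case (b) remains even if own baseline is taken to mean the average.

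**Length of the delay.** In a missed case the first value is below B + 0.3 and the retest is at least B + 0.4, so the retest is the higher of the two. The first value already exceeded the trigger, so the retest exceeds it too and calls for another retest. On the literal reading, the first retest now serves as the qualifying first observation. If the rise is still at least 0.4 at the next draw, the stop is met about 6-10 days after the triggering value instead of 3-5. The difference is one cycle. If creatinine has fallen below that level by then, the literal rule does not stop the participant.

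**The case against.** The strongest reply is that the literal reading is strained. The Action cell orders a retest and then speaks of the second assessment. Taken in sequence, that is simply the retest, and the parenthesis only points back to the test that triggered it. On that reading both cases stop at the first retest and nothing is delayed. This stands as a plausible reading, but the row does not say that it is the intended one.

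A second reply is that own baseline may mean the participant's pre-dose reference, which the adjacent cell sets as the average. Section 8.2.2 describes baseline only as before receipt of the product, and SAP Section 6.3.2 is a reporting rule that does not instruct sites. This reading would close case (a). It would not close case (b).

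Third, the bands are narrow. If creatinine were reported only to 0.1 mg/dL (an assumption), the worked pairs would be empty: 0.70/0.80 needs a first value above 1.05 and below 1.10, and 0.50/0.50 needs one above 0.75 and below 0.80. Other pairs would still leave a gap. For example, 0.6/0.9 has an average of 0.75, and a first value of 1.1 is +0.35 over the average but +0.2 over baseline.

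Fourth, safeguards exist. Under Section 7.2 a participant "may be withdrawn at any time at the discretion of the investigator for safety". Section 8 adds: "Immediate safety concerns should be discussed with the sponsor immediately upon occurrence or awareness". Section 8.2.2 has clinically significant abnormal tests repeated. These limit the harm, although they do not replace a clear numerical stop.

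**Conclusion.** The mismatch between the two cells is certain from the text. The delayed stop is conditional: it needs the literal reading together with pre-dose and first values inside one of the two bands. Where it occurs, its size is about one further retest cycle, ideally 3-5 days. How often that would be cannot be estimated from the documents. Severity is minor. Power, alpha and the planned analyses are not touched by the defect.

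Two stronger readings are tempting and are not supported:
- **That the rule leaves participants with a sustained renal rise on treatment indefinitely.** Every missed retest value itself triggers another retest, and discretion to withdraw applies throughout.
- **That the retest triggers are also faulty because, with baseline below screening, a sizeable rise over own baseline may call for no retest.** With 1.10 and 0.80, a value of 1.21 is +0.41 over baseline but +0.26 (27%) over the average of 0.95. That is a separate matter. The value is only 0.11 above screening, and averaging two pre-dose values may be a deliberate way to damp a low baseline. The documents give no ground for calling it an error.

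**What to change.** Leave the Condition cell as it is. In the Action cell, delete the parenthetical precondition and write: *If, on retest after either trigger, serum creatinine is ≥0.4 mg/dL (≥35.4 µmol/L) above the participant's own baseline measurement, discontinue.* The follow-up and supportive-care wording stays.

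Both worked cases then stop at the first retest: 1.22 − 0.80 = 0.42 and 0.92 − 0.50 = 0.42. Own baseline is the only reference that the Action cell names, and no stop under that reading is lost.

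The cost is wording in one table row and some additional stops compared with the literal rule, all at the sponsor's own threshold. Their number cannot be estimated. Each extra stop removes a participant from the study, and a missing Week 24 remission value is generally counted as non-response (Section 9.4.1). If PF-06650833 raises creatinine, such stops would fall more on the arms that contain it.

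There is one trade-off. A site that now reads the 0.4 level against the average would lose some stops when baseline is above screening. With 0.70 and 0.80, for example, a retest of 1.17 is +0.42 over the average but +0.37 over baseline. Changing the retest triggers as well would override the sponsor's averaging and is not needed to close this gap.

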
* The participant must return to the study site for prompt retesting and include the following tests: albumin, creatine kinase (CK), total bilirubin, direct and indirect bilirubin, GGT, PT/INR, and alkaline phosphatase.
 
Additional investigations include a detailed history, occupational exposure, sexual history, travel history, history of contact with a jaundiced person, surgery, blood transfusion, history of liver or allergic disease, work exposure, history of ethanol, recreational drug and dietary supplement consumption. Testing for acute hepatitis A, B or C infection and biliary tract imaging may be considered. A participant with a total bilirubin value ≥2 × ULN concurrently may need to return to the investigational site and be evaluated as soon as possible, preferably within 48 hours from awareness of the abnormal results (refer to Appendix 6).
	

Condition	Action
Hematology	
Neutrophil counts <1000 cells/mm ³ .	The participant should return to the study site for prompt retesting, ideally within 3-5 days .
Platelet counts <100,000 platelets/mm ³ .	The participant should return to the study site for prompt retesting, ideally within 3-5 days .
Lymphocyte counts <500 lymphocytes/mm ³ .	The participant should return to the study site for prompt retesting, ideally within 3-5 days .
Any single hemoglobin value <8.0 g/dL or one that drops ≥ 2 g/dL below baseline.	The participant should return to the study site for prompt retesting, ideally within 3-5 days .
Two sequential hemoglobin values <8.0 g/dL or a decrease of more than 30% from baseline value.	Treatment with all study drugs will be discontinued and the participant withdrawn from this study. Participant followed until resolution or deemed medically stable by PI.
Two sequential platelet counts <75,000 platelets/mm ³ .	Treatment with all study drugs will be discontinued and the participant withdrawn from this study. Participant followed until resolution or deemed medically stable by PI.
2 sequential neutrophil counts <1000 cells/mm ³	Treatment with all study drugs will be discontinued and the participant withdrawn from this study. Participant followed until resolution or deemed medically stable by PI.
Confirmed lymphocyte counts <500 lymphocytes/mm ³ by repeat testing.	Treatment with all study drugs will be discontinued and the participant withdrawn from this study. Participant followed until resolution or deemed medically stable by PI.
Infections	

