10.6. Appendix 6: Liver Safety: Suggested Actions and Follow-up Assessments

Potential Cases of Drug-Induced Liver Injury

Humans exposed to a drug who show no sign of liver injury (as determined by elevations in transaminases) are termed “tolerators,” while those who show transient liver injury, but adapt are termed “adaptors.” In some participants, transaminase elevations are a harbinger of a more serious potential outcome. These participants fail to adapt and therefore are “susceptible” to progressive and serious liver injury, commonly referred to as drug-induced liver injury (DILI). Participants who experience a transaminase elevation above 3 times the upper limit of normal (\times ULN) should be monitored more frequently to determine if they are an “adaptor” or are “susceptible.”

In the majority of DILI cases, elevations in aspartate aminotransferase (AST) and/or alanine aminotransferase (ALT) precede total bilirubin (TBili) elevations ($>2 \times$ ULN) by several days or weeks. The increase in TBili typically occurs while AST/ALT is/are still elevated above $3 \times$ ULN (ie, AST/ALT and TBili values will be elevated within the same laboratory sample). In rare instances, by the time TBili elevations are detected, AST/ALT values might have decreased. This occurrence is still regarded as a potential DILI. Therefore, abnormal elevations in either AST OR ALT in addition to TBili that meet the criteria outlined below are considered potential DILI (assessed per Hy’s law criteria) cases and should always be considered important medical events, even before all other possible causes of liver injury have been excluded.

The threshold of laboratory abnormalities for a potential DILI case depends on the participant’s individual baseline values and underlying conditions. Participants who present with the following laboratory abnormalities should be evaluated further as potential DILI (Hy’s law) cases to definitively determine the etiology of the abnormal laboratory values:

- Participants with AST/ALT and TBili baseline values within the normal range who subsequently present with AST OR ALT values $>3 \times$ ULN AND a TBili value $>2 \times$ ULN with no evidence of hemolysis and an alkaline phosphatase value $<2 \times$ ULN or not available.

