- For participants with baseline AST **OR** ALT **OR** TBili values above the ULN, the following threshold values are used in the definition mentioned above, as needed, depending on which values are above the ULN at baseline:
 - Preexisting AST or ALT baseline values above the normal range: AST or ALT values >2 times the baseline values AND $>3 \times$ ULN; or $>8 \times$ ULN (whichever is smaller).
 - Preexisting values of TBili above the normal range: TBili level increased from baseline value by an amount of at least $1 \times$ ULN **or** if the value reaches $>3 \times$ ULN (whichever is smaller).

Rises in AST/ALT and TBili separated by more than a few weeks should be assessed individually based on clinical judgment; any case where uncertainty remains as to whether it represents a potential Hy's law case should be reviewed with the sponsor.

The participant should return to the investigator site and be evaluated as soon as possible, preferably within 48 hours from awareness of the abnormal results. This evaluation should include laboratory tests, detailed history, and physical assessment.

In addition to repeating measurements of AST and ALT and TBili for suspected cases of Hy's law, additional laboratory tests should include albumin, creatine kinase (CK), direct and indirect bilirubin, gamma-glutamyl transferase (GGT), prothrombin time (PT)/international normalized ratio (INR), total bile acids, and alkaline phosphatase. Consideration should also be given to drawing a separate tube of clotted blood and an anticoagulated tube of blood for further testing, as needed, for further contemporaneous analyses at the time of the recognized initial abnormalities to determine etiology. A detailed history, including relevant information, such as review of ethanol, acetaminophen (either by itself or as a coformulated product in prescription or over-the-counter medications), recreational drug, supplement (herbal) use and consumption, family history, sexual history, travel history, history of contact with a jaundiced person, surgery, blood transfusion, history of liver or allergic disease, and potential occupational exposure to chemicals, should be collected. Further testing for acute hepatitis A, B, C, D, and E infection and liver imaging (eg, biliary tract) and collection of serum sample for acetaminophen drug and/or protein adduct levels may be warranted.

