All cases demonstrated on repeat testing as meeting the laboratory criteria of AST/ALT and TBili elevation defined above should be considered potential DILI (Hy's law) cases if no other reason for the liver function test (LFT) abnormalities has yet been found. **Such potential DILI (Hy's law) cases are to be reported as SAEs, irrespective of availability of all the results of the investigations performed to determine etiology of the LFT abnormalities.**

A potential DILI (Hy's law) case becomes a confirmed case only after all results of reasonable investigations have been received and have excluded an alternative etiology.

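### Section 8.11 has no mandatory dosing action when a single AST/ALT above 3 x ULN has fallen below 3 x ULN at retest but total bilirubin is at least 2 x ULN (cheap improvement)

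*Protocol*

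**What the plan says.** Protocol Section 8.11 has four liver rows that end in discontinuation of all study drugs and withdrawal. The first requires "2 sequential AST or ALT elevations ≥3 x ULN with a total bilirubin value ≥2 x ULN". The second and third keep the same pair of AST/ALT values and replace bilirubin with a raised INR or with hepatic symptoms. The fourth needs two sequential values of at least 5 x ULN and nothing else.

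A fifth row covers a single AST or ALT above 3 x ULN. Its action is a retest, ideally in 3 to 5 days. Its footnote says "The participant must return to the study site for prompt retesting and include the following tests", and the list that follows includes total bilirubin and PT/INR. A concurrent bilirubin of at least 2 x ULN may call for a return visit, preferably within 48 hours. Neither the row nor the footnote mentions dosing.

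Appendix 6 (Section 10.6) describes the sequence at issue: "In rare instances, by the time TBili elevations are detected, AST/ALT values might have decreased. This occurrence is still regarded as a potential DILI". Its instructions concern evaluation ("The participant should return to the investigator site and be evaluated as soon as possible, preferably within 48 hours"), repeat and additional tests, and SAE reporting. None concerns dosing.

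Section 7.2 states: "Any participant who meets discontinuation criteria as specified in" Section 8.10 should be discontinued. Section 8.10 points only to the table in 8.11.

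**The concern.** The stop rules and the liver appendix do not line up. Appendix 6 recognises that transaminases can already be falling when bilirubin rises, and it keeps such a case under suspicion. Section 8.11 makes every stop conditional on the second transaminase value still being high. A participant whose bilirubin climbs while AST/ALT falls back drops out of the stop rules at the point where Appendix 6 says the suspicion remains.

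The stake is individual safety. Section 2.3 names liver transaminase effects as possible for PF-06650833, Section 2.2.5.3 lists transaminase increases for tofacitinib, and potential Hy's law cases are a listed safety endpoint in Section 3. Section 4.2 calls the trial an initial exploration of the combination, at maximal doses. For this pattern, whether blinded drug continues during the work-up depends on someone choosing to stop it.

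**Working it through.** This is a question of rule coverage. The plan gives no figure to reproduce, and sample size, power and alpha play no part.

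**Step 1: the rows as conditions.** Let A1 and A2 be AST or ALT at the first sample and the retest, and B total bilirubin, all in multiples of ULN.

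- Row 1: A1 ≥ 3 and A2 ≥ 3 and B ≥ 2
- Row 2: A1 ≥ 3 and A2 ≥ 3 and INR raised
- Row 3: A1 ≥ 3 and A2 ≥ 3 and hepatic symptoms
- Row 4: A1 ≥ 5 and A2 ≥ 5
- Row 5: A1 > 3, retest only

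Every stop row contains A2 ≥ 3 or A2 ≥ 5. If A2 is below 3, all four fail whatever A1, bilirubin, INR or symptoms may be. This follows from the wording; the values below only illustrate it and carry no information on frequency.

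| A1 | A2 | Bilirubin (first, retest) | INR and symptoms at retest | Result under 8.11 |
|---|---|---|---|---|
| 3.5, 6 or 9 | 2.0 or 2.9 | 1, 2.5 or 2.5, 2.5 | absent or present | retest row only |
| 3.5, 6 or 9 | 3.2 | 1, 2.5 or 2.5, 2.5 | absent | row 1 stops |
| 3.5, 6 or 9 | 3.2 | 1, 2.5 or 2.5, 2.5 | present | rows 1, 2 and 3 stop |

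The outcome turns on the second transaminase value alone. Bilirubin of 2.5 x ULN at both samples, with raised INR and symptoms, still triggers no stop when A2 is 2.9.

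**Step 2: can the pattern be seen?** Yes. The retest required by the footnote includes total bilirubin and PT/INR.

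**Step 3: does another section supply a mandatory action?**

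- Section 7.2, through 8.10, leads back to 8.11. Its other route is withdrawal at the investigator's discretion.
- Section 8 directs immediate safety concerns to the sponsor for a decision on continuing treatment. That is a directed discussion with an open outcome.
- Appendix 6 prescribes evaluation, repeat tests and reporting.
- Section 8.2.2 asks for clinically significant results to be repeated until normal or baseline.
- Sections 8.3.6.3 (adjudication) and 9.5.1 (periodic unblinded review) do not govern one participant's next dose.

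None of these automatically holds or stops drug.

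**The case against.** The strongest reply is that 8.11 consistently confirms before stopping: creatinine, hemoglobin, platelets, neutrophils and lymphocytes all need a repeat result before laboratory-based discontinuation. Around that sit evaluation within about 48 hours, sponsor discussion, adjudication and unblinded monitoring. A competent investigator would often stop drug anyway. This stands as a limit on severity. It does not remove the mismatch, because here the repeat test can confirm the bilirubin signal and the rules still call for nothing. Holding first is also not foreign to 8.11: for suspected venous thromboembolism, treatment is withdrawn while the event is being confirmed.

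Three stronger readings are tempting, and the documents do not support them.

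- **Dosing would run on to the next scheduled chemistry.** With 28 days between visits from Week 4 and a retest at 3 to 5 days, a reader might count 28 - 5 = 23 to 28 - 3 = 25 further doses, or 82 - 60 - 5 = 17 to 88 - 54 - 3 = 31 with the ±3-day windows. That assumes Appendix 6 is ignored. It asks for prompt evaluation and repeat AST, ALT and bilirubin, so these counts are a worst case and no measure of the gap.
- **Nobody need decide whether this is a Hy's law case.** Appendix 6 does say "All cases demonstrated on repeat testing as meeting the laboratory criteria of AST/ALT and TBili elevation defined above should be considered potential DILI", which fits this pattern less clearly, and it adds: "Rises in AST/ALT and TBili separated by more than a few weeks should be assessed individually based on clinical judgment". But that same sentence sends any case of remaining doubt to the sponsor, and the appendix treats elevations meeting its criteria as important medical events before other causes are excluded.
- **Section 6.6 forbids a liver hold.** It bars changes to the dosing schedule, but Section 7.2 contemplates interruptions in response to an AE and requires withdrawal only beyond 7 consecutive days.

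**Conclusion.** The point holds as a cheap safety improvement. No mandatory hold or stop applies when one AST/ALT above 3 x ULN is followed by a retest with AST/ALT below 3 x ULN and total bilirubin at or above 2 x ULN, although Appendix 6 regards a bilirubin rise after transaminases have fallen as potential DILI. The gap is the lack of a required dosing action; detection, work-up and the power to stop drug are all present.

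The conclusion rests on reading the stop rows literally, so that a second value below 3 x ULN fails the sequential condition. Appendix 6 describes the pattern as rare and the documents give no frequency, so no expected number of cases or doses is offered. The efficacy analyses are untouched apart from the side effect noted with the fix.

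**What to change.** Add one liver row to 8.11 and leave the existing rows unchanged.

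- **Condition:** AST or ALT above 3 x ULN with total bilirubin at or above 2 x ULN in the same sample or at the retest, even if AST/ALT has since fallen below 3 x ULN. Use the Appendix 6 thresholds when baseline is abnormal, apply its qualifiers on hemolysis and alkaline phosphatase, and use direct bilirubin in known Gilbert's syndrome, which exclusion 25 allows into the trial.
- **Action:** hold all study drugs on awareness and evaluate per Appendix 6, preferably within 48 hours. Discontinue if bilirubin remains at or above 2 x ULN on repeat with no alternative cause found; otherwise dosing may resume with the sponsor's agreement.

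The bilirubin cut-off should be at or above 2 x ULN, as in row 1; a strict inequality would miss a retest of exactly 2.0. In Section 6.6, add a cross-reference saying that the AE-driven interruptions contemplated in 7.2 include this hold.

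Illustrations (x ULN, normal baseline, qualifiers met):

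- ALT 6 then 2.9, bilirubin 1 then 2.4: hold at the retest. A further bilirubin of 2.3 with no other cause leads to discontinuation; 1.2 lets dosing resume if the sponsor agrees.
- ALT 4 then 1.5, bilirubin 2.4 then 1.1: hold at the first sample; dosing may resume after the second with the sponsor's agreement.
- ALT 6 then 2.0, bilirubin 1 throughout: no hold.

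The cost is one table row and one cross-reference by amendment. Bilirubin is already measured at retest and the evaluation is already requested, so no scheduled visit is added. The downside is a few short holds. Any that exceed 7 consecutive days would lead to withdrawal under 7.2 and could count as Week 24 non-response under Section 9.4.1. If dosing has finished, the row belongs in the forthcoming Phase 3 protocol mentioned in Amendment 3.
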